- 2. Do nothing if they do not wish to take part it will be assumed that they do not want to take part if a consent form is not received within 2 weeks
- 3. Call Clinical Research Network for more information and/or to complete consent form over the phone

Potential participants are asked to complete consent forms withing one week if they would like to take part. If nothing is received after 2 weeks, they will be removed from the study invite lists by GP practices.

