4.2 Pseudonymised data content

At the end of the pseudonymised data collection phase, we will have drawn from 4 main sources for each participant:

- a. Pseudonymised data drawn from wearables, sensors, devices and monitors
- b. Pseudonymised related data drawn from several NHS sources
- c. Geographically related data drawn from environmental sources (MetOffice, DEFRA)
- d. Pseudonymised participant (with multiple morbidities) related questionnaire results including participant outcome measures

Pseudonymised data drawn from wearables, sensors, devices and monitors – individual participant specific (anonymised) data which will include: See table B above.

a. Pseudonymised patient data drawn from NHS including:

- GP or HCP attendances (or visits) in the period of study and would include reason for attendance
- NHS Hospital Episode Statistics (HES) data for South Lincolnshire, containing details of all
 admissions, outpatient diagnoses and A & E attendances, together with GP data records
 for the whole patient group for the 2 years preceding the study together with the study
 period and one year into the future to evaluate impact.
- Known procedures (OPCS, SNOMED CT, etc.)
- Prescribed drugs and changes in the period of the study (and make this for 2 year preceding the study and one year into the future).
- GP Data and Social Prescribing Data.
- Post code or postcode sector of patients to facilitate linkage to the deprivation index (IMD) and environmental data.
- Death or other severe events

19

b. Data drawn from environmental sources will include:

- Air quality and weather pollutant levels e.g. temperature, dew point, etc.
- Postal sector of pseudonymised patients
- c. QuestLink questionnaires at intervals including:
 - HowRu and Health Confidence Score (HCS) Person Reported Measures of Outcomes
 - Questions about events in the family
 - Medication related questions including use of "over the counter medications"
 - Activity levels

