5.2 Data analysis

The use of Artificial Intelligence (AI) is being increasingly used as predictive healthcare solutions to provide early detection of long term conditions that anticipate and can thereby prevent illness and disease. One such common example of this technology used for screening is Atrial Fibrillation (AF) which utilises Artificial Intelligence techniques such as Principal Component Analysis (PCA) and Neural Networks (NN) (Ref Braun 2018). Artificial Neural Networks (ANNs) provide a powerful technique for modelling complex non-linear relationships for classification. Neural Networks are commonly applied in non-linear predictions to analyse the complex relationships and correlation that exist between patient history including the social determinants of health, and development of future conditions, and also between the physiological and behavioural measurements.

The NHS has the great advantage of having vast amounts of historic patient data in standardized form suitable for analysis and AI training. The Healthcare industry is data-rich, but it is not always possible to extract the required information from the data in a timely manner or in a manner that is useful to the patient or healthcare professional.

As a separate part of the study (phase 2) we intend to make assessments of the likely qualitative and economic benefits of the predictive system based on the data collected. These will be tested through data quality evaluation, model selection, training data categorisation, leaning algorithm(s), sensitivity and specificity analyses to help determine the confidence of the predictive systems (Ref: Longstaff 2010). The benefits can accrue in several parts of the "services". We will attempt to define the proportions in each.

Benefits will accrue to the patient, the family and work; they will also accrue to the health and social services when the specific event or illness is avoided. We will study trends across the cohort that were part of the PoC (patient participation groups PPG) compared with a similar cohort of patients that were not part of the PoC (patients reference group PRG) and report on the findings.

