The design of the input data set requires the size of the data set to be defined. A larger data set will require more time to train the machine learning algorithms. The balance between learning capability and learning time will be considered and set with outcome requirements. The methodologies for the clinical components are based on existing implementations of Neural Networks for preliminary diagnosis to support targeted screening in the NHS.

Developing of machine learning algorithms can be split broadly into five stages.

24

- a) Obtain data that is pseudonymised and consists of a representative cross-section of patients with and without the condition or an adverse event
- b) Reduce the number of feature parameters that are relevant using de-correlation methods such as Primary Component Analysis (PCA)
- c) Split the data for machine learning training, monitoring of overfitting and performance testing to facilitate evaluation of prediction quality and applicability
- d) Train various machine learning models and topologies to evaluate which combination works best for the required predictions
- e) At the end of the study, device data will be connected to primary and secondary care data to build full medical records of participating patients. Such longitudinal medical records facilitate the prediction of future events to deliver pro-active care.

Joining the Device Data with GP and Hospital data requires a consistent key across all three data sets. Depending on the data structures held at Arden and Gem (AGEM) CSU, the Trial IDs can be mapped to a clear either to clear or pseudonymised NHS number, with a preference for pseudonymised NHS numbers.

GP and Hospital data extraction will be performed by applying the list of participating patients as a filter. This filter will be the list of pseudonymised NHS number where possible. The resulting data structure will be a collection of clinical and non-clinical data sets that can be linked via a pseudonymised primary key, or NHS number, location and calendar date for air pollution or weather data. **See table E – above**

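### Section 5.2 commits to comparing participants with a non-participant reference group, but its written extraction rule admits participants only, so the extracted and linked data set holds no reference-group data

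*Protocol*

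**What the plan says.** Three statements in the Protocol bear on this point.

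- **The comparison (section 5.2).** In the text on the benefits of the predictive system, the plan says that trends in the participating cohort (PPG) will be set against "a similar cohort of patients that were not part of the PoC (patients reference group PRG"). It commits to reporting the result. It gives no size, source or selection rule for the PRG.
- **The extraction rule (section 5.2, after the five stages of algorithm development).** "GP and Hospital data extraction will be performed by applying the list of participating patients as a filter". On the key, it adds: "This filter will be the list of pseudonymised NHS number where possible". The preceding stage (e) gives the purpose as connecting device data to care data "to build full medical records of participating patients".
- **The data content (section 4.2).** The opening says that "we will have drawn from 4 main sources for each participant". One item beneath it is HES data for South Lincolnshire, with GP records, "for the whole patient group for the 2 years preceding the study", continuing through the study period and for one further year so that impact can be evaluated.

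**The concern.** A filter on participants cannot return anyone defined as a non-participant. If the extraction is run as written, the planned comparison has data on one side only. Without PRG history, nobody can show that the two cohorts were similar at the start. Without PRG events during and after the study, there is no trend to compare.

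This is not an analysis detail that can wait for a statistical analysis plan. Whose records may be pulled is settled in the data-access application and the extraction specification, and an analysis plan cannot recover records that were never requested.

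There is a secondary risk. If PRG data are found later from whatever source is at hand, the two groups may have been counted from different sources, and a difference in contacts could then reflect ascertainment. The documents give no figures from which to size that risk.

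**Working it through.** The plan gives no figure to reproduce, and no formula applies beyond a count. The check sets the statements side by side.

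1. **Who is on the filter list.** Participants only. The recruitment target is 500 (section 3.1), so the list holds at most about 500 people.
2. **Who is in the PRG.** Patients outside the PoC (section 5.2). The overlap with the filter list is empty by definition.
3. **What the rule yields.** PRG records passing the filter = 0, against up to 500 participants.
4. **Over what period.** Section 4.2 gives two years before, the study period (about six months, section 1.3) and one year after: 24 + 6 + 12 = about 42 months. The PRG count is 0 in each window.
5. **Whether another written route supplies PRG data.**
   - Section 3.2.1 searches HES on pseudonymised non-participants, but to build the list of people to approach. Section 5.1.1 describes the same tool, again for finding the cohort. Neither says that these records are kept as reference-group outcomes.
   - Section 3.3.1 says of people who do not reply that "they will be removed from the study invite lists by GP practices". This concerns invitations. It neither makes them the PRG nor rules them out.
   - Section 5.3 mentions a data-access application still to be completed and possible use of GPES data in connection with the pandemic. It does not mention a PRG extract.
6. **Whether section 4.2 fills the gap.** There are two readings:
   - The whole patient group means all participants, which fits the per-participant opening of the list. The PRG then has no data.
   - It means the area population, which fits the reference to South Lincolnshire and the stated aim of evaluating impact. PRG data would then exist, but the item contradicts the filter in section 5.2.

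On either reading, sections 4.2 and 5.2 cannot both stand beside the comparison as worded.

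**The case against.** The strongest reply is that the filter sentence belongs to the device-linkage step. It follows stage (e) and the text on a common key for device, GP and hospital data. PRG members have no devices and would never belong in that set. The protocol does not say that this is the study's only extraction, and the contents of the data-flow tables (D to F) are not visible in the text reviewed, so a PRG flow could be drawn there. Data access is also openly unfinished: section 1.3 leaves information-governance permissions for phase 2 to be arranged, and section 5.3 leaves the data-access application to be completed.

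Much of this stands. It limits the point to the written rule and to the set which that rule produces. It does not remove the conflict, because the sentence speaks of GP and hospital extraction without qualification, and no other text gives the PRG a source.

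A reader might go further in three ways that the documents do not support:

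- **That no PRG data could exist anywhere in the study.** The area-wide reading of section 4.2 and the unseen tables prevent that conclusion.
- **That GP records are out of reach for people who did not consent.** No section says so. Section 1.3 lists GP data among details already held in NHS databases and analysed in de-identified form, and the pre-consent restriction in section 3.2.1 covers identifiable data only. The most that can be said is that no route is stated.
- **That the PRG would be counted from hospital data alone, with a shortfall of a known size.** The protocol never proposes a hospital-only PRG and gives no split of contacts by source.

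**Conclusion.** The concern holds as a conflict between a stated extraction rule and a stated analysis. Followed literally, the rule gives a linked set with 0 PRG records against up to 500 participants over about 42 months, and the promised comparison cannot be made from it. This rests on reading the extraction sentence as written and on no PRG flow appearing in the data-flow tables. If such a flow exists, the text still needs to be aligned with it.

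The point should be corrected, but it does not threaten the study's main aim. The comparison belongs with the benefits assessment that section 5.2 places in phase 2. Prediction within participants, which carries the hypothesis in section 2.1, uses participant data and is not affected.

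**What to change.** Reconcile the comparison and the filter in section 5.2 with the data list in section 4.2:

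1. State that the participant filter applies to the device-linkage step.
2. Add a second pseudonymised extraction for a PRG list drawn from the same HES stratification search that builds the recruitment list, over the same windows (two years before, study period, one year after). State the size of that list. The plan seeks at least 700 candidates for 500 places, so at full recruitment the remainder could be as small as 700 − 500 = 200, and the search may need to return more.
3. Define the whole patient group in section 4.2 so that it agrees with items 1 and 2.
4. Name the PRG extraction in the data-access application that section 5.3 leaves open.
5. Limit the PPG–PRG comparison to outcomes captured from the same sources in both groups: HES admissions, A&E attendances and outpatient activity. Include GP contacts only if a pseudonymised GP extract is obtained for both.

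If the second extraction is not wanted or not permitted, delete the comparison.

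The cost is protocol wording, one extra pseudonymised data pull with its governance basis, and possibly a narrower set of compared outcomes. It is cheapest to do before the data-access application is completed.

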5.3 Results and Project closure (see Table D: Data flows)

The CCG's commercial cloud-based platform (Philips Healthsuite) purpose-built for health, will collect participant data in an easy and scalable way through sensor based wearables, software based sensors using the camera on a smart phone or tablets and web based questionnaires. The data will be ingested and stored. Data scientists and researchers will be able to perform their data analysis and model development within the secure cloud based platform using the Workbench. This provides a collaborative development environment with tools like RStudio, Jupyter Notebooks and TensorFlow and manages the end-to-end process of analytics, analytics asset creation, deployment and support. It will comply with the Code of Practice on Confidential Information for data collection, transfer, storage, processing & destruction throughout the PoC.

We are already having informal discussions with the Data Access Request Services (DARS). Once we have received approval for the study we will complete our application to them together with consideration of the GPES data for pandemic data.

The data will be securely stored by Arden and Gem CSU at the completion of the study.

5.4 Study Steering Group

A Study Steering (SSG) will oversee the organisation, the data quality and the output of the study. The steering group will oversee the data flows and management. To aid them they will use make use

25

of a monitoring device that ensures the correct and consistent correlation of the participant's PoC study number with the ID number of the wearable, sensor and monitor; and will generate a warning of any inconsistency.

Table F below illustrates the flow of data in the analytic phases of the PoC Smart Technology DataStudy Trial:

Phase 1 with the flow from the physiological and behavioural data mainly but with QuestLink data also

- Phase 2 with the additional data from the clinical health and social care data, together with Air quality
- Predict events Phase 1 with the "predict events" data
- Budget Phase 1 with the budget data linked to the relevant phases and support the development of the transformation report

Commented [CP8]: Needs rewording to fit with new study stages Data Collection Analysis Results

6. Ethical Considerations

Due to Covid-19, consenting processes have been adapted to ensure that consent is undertaken remotely. We considered adopting electronic means but have now decided to adopt a modified paper based system which has produced good results and with which the LCRN are familiar.

The research team will provide GP Practices with the following "participant facing documents" to use in recruitment activities with their own patients:

1. Participant Invitation Letter

26

IRAS ID: 286225	[Proof of Concept – Smart Technology – South Lincolnshire]
CPMS: 44344	PoC Protocol Version: 1.4
01/08/2020	

This will give a brief summary of the study and instructions on how to either accept or decline the invitation.

2. Participant Information Sheet (PIS)

This will provide a more detailed explanation of the study including what the participant will need to do, why we are undertaking the study, how they can withdraw from participation etc. a copy of the PIS has been submitted with this application.

3. Study Consent Form

This will be the formal consent form that participants will sign to agree to take part in the study. Due to Covid-19, consenting processes have been adapted to ensure that consent is undertaken remotely. The Clinical Research Network have confirmed that the consent form can be posted to participants as part of the initial communication. Prior to Covid-19, consent would have been obtained in a face to face meeting with a healthcare professional.

4. Decline to Participate Return Slip

This will allow a participant to advise the GP practice if they do not wish to take part in the study.

The GP practice will send the information pack above to each potential participant and include a prepaid return envelope for them to return their signed consent form or decline to participate return slip.

The participant will be given three options:

- 1 Sign and return the consent form if they are happy to take part
- 2 Sign and return the *Decline to Participate Return Slip* if they do not wish to take part
- 3 Wait for a telephone call from the GP practice if they require further information before deciding

Patients will then be given one week to decide whether they want to take part before further contact is made with them. After a week has passed, a healthcare professional from their GP practice will call them to discuss the study and if the patient is still unsure, they will be given longer to consider.

More detailed descriptions of the consenting processes is contained in the Consent and Patient Information Sheet (PIS). It will be made very clear to the participants that:

- a) their usual care will continue as usual if they agree to join PoC;
- b) they will not gain any particular benefit for themselves in health terms but they will be helping others. They will understand that they understand that the PoC is an "observational study";
- c) there will be support on offer to them during the trial by messaging electronically, or by phone and speaking to one of our helpers;
- d) they can withdraw from the trial at any time without the need to give a reason; their pseudonymised data cannot be removed and will continue to be used;

27

IRAS ID: 286225[Proof of Concept – Smart Technology – South Lincolnshire]CPMS: 44344PoC Protocol Version: 1.401/08/2020

- e) should they become unwell and lose capacity they will not continue in the research study but their pseudonymised data will be retained and used in the study;
- they will be informed that the PoC has been approved by the Health Research Authority, which includes Research Ethics Committee review;
- g) they will be informed of the outcomes of the PoC at the end of the study;
- h) they will be informed that their data being used in the PoC is pseudonymised and they cannot be identified.

Their own GP will not be able to see this pseudonymised data. We will NOT be using face-to-face methods because of precautions to Covid-19. Instead we will be using "participant facing documents" to use in recruitment activities, to explain the study and will be encouraging questions, with the intent of ensuring that they are fully informed in some detail.

From the moment the participant agrees to join the trial, and for the duration of the trial, the participants data will be pseudonymised; the participant will have understood this when they agree to consent.

7. Monitoring and auditing the study

The Chief Investigator (CI) will ensure there are adequate quality and number of monitoring activities conducted by the study team. This will include adherence to the protocol, procedures for consenting and ensuring adequate data quality.

The Chief Investigator will inform the Sponsor should concerns arise from monitoring activities, and/or if there are problems with oversight/monitoring procedures.

8. Training

The Chief Investigator/ Coordinator will review and provide assurances of the training and experience of all staff working on this study. Appropriate training records will be maintained in the study site files. A copy of these documents will also be kept at the Sponsor Site. Site inductions will be undertaken by the CI and coordinator in order to train local staff.

9. Assessment and Management of Risk

The following represents a table listing potential risks and mitigations:

Risks	Mitigation
Electrical risk	ActivInsights device is CE Marked and is approved by NHS for Research. Other devices are apps and non-wearable.

28

 IRAS ID: 286225
 [Proof of Concept - S

 CPMS: 44344
 PoC Prote

 01/08/2020
 PoC Prote

[Proof of Concept – Smart Technology – South Lincolnshire] PoC Protocol Version: 1.4 **Commented [CP9]:** Needs rewriting to remove the repeated information from recruitment section above and replace with: Considerations related to:

- Covid-19

- Covid-19
 Non-interventional collection of data and blinding of
- results to participants
- How care home staff will be asked to participate (refer to SOP)
- Any other ethical considerations

Misreading of physiological data	Observational study with no clinical intervention
Vulnerable Patients	CRB Certified support staff at Optima
Data / IG Breach	Following expert advice from NHS X DARS
	RESEARCH team together with Optum IG and
	AGEM CSU Team

10. Protocol Deviations and Violations

A deviation is usually an unintended departure from the expected conduct of the study protocol, which does not need to be reported to the sponsor. The Chief Investigator will monitor protocol deviations.

A protocol violation is a breach which is likely to effect to a significant degree:

- a) the safety or physical or mental integrity of the participants of the study (not applicable in this study); or
 - b) the scientific value of the study.

The Chief Investigator and Sponsor will be notified immediately of any case where the above definition applies during the study conduct phase.

11. Recording Adverse Events/ Serious Safety Measures

In the event of an Adverse event, the following information will be recorded and protocol will be followed overseen by the Senior Responsible Officer for South Lincolnshire CCG – [name] & The Chief Investigator – [name].

Date	Nature of the event	Reported to:	Action taken recorded	Resolution agreed by

12. Reporting and dissemination

Results will be fed back initially to the Study Steering Committee, and subsequently to any associated funding bodies. Results of any studies will be presented at scientific meetings and disseminated in the form of scientific papers.

29

13. References

Benson T, Sizmur S, Whatling J, et al Evaluation of a new short generic measure of health status: howRu.
J Innov Health Inform 2010;18:89–101 .doi:10.14236/jhi.v18i2.758

Coulter A Measuring what matters to patients. BMJ 2017;356 ...doi:10.1136/bmj.j816

